### **VISIT #2**

#### **5.5. Labor Induction and Labor**

Management of the subject after the initial 12 hours of pre-induction or following the earlier removal or spontaneous expulsion of the dilator will be the same for both groups and at the discretion of the clinical team. Additional ripening (mechanical or prostaglandins) and/or oxytocin may or may not be needed. If needed, duration, type and dose of additional ripening agents and oxytocin will be documented.

Routine intrapartum care will be provided and relevant data collected by the subject's managing obstetrical team.

Trained and experienced research staff will be responsible for all research data abstraction. The PI and collaborators will review and validate the outcomes. If there is uncertainty, a second investigator will review the chart, discuss with the other investigators as needed, and make a final determination regarding the outcome.

Subjective assessment data will be collected, using adequate validated tools either after Dilapan-S® extraction or any time prior labor or post-partum (Appendix 3) at the time point best suitable for both the subject and the study team.

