## 5. Study Procedures

### VISIT #1

#### 5.1. Screening, eligibility assessment, consenting and baseline data collection

After institutional review board (IRB) approval, pregnant women who have a plan of care for induction of labor at term will be approached by the principal investigator or any of the co-investigators for participation in the study. Informed consent for this study can be obtained during several different phases of interaction with the patient:

Phase 1: At any antenatal obstetrical office visit when decision is made to schedule subject for induction of labor.

Phase 2: Potential subjects presenting for induction of labor at term in the “Labor and delivery” unit (L&D).

Subjects willing to participate in the study will be evaluated for their eligibility including their Bishop score. The latter will be obtained from the medical record after the initial pelvic exam which is standard of care in our unit. Subjects will be reassured that participation in the study is voluntary and will not interfere with diagnosis or treatment of her condition. The subjects will receive the same care and expertise as any other subject treated in our unit. Subjects are approached in a private patient room, and written consent will be obtained by direct person-to-person contact. The principal investigator, study coordinator, or a collaborator will be responsible for the informed consent. Non-English-speaking subjects are anticipated to be part of the study population and informed consent will be provided in their primary language. We will also be using the teach back method; briefly the potential subject will be asked to explain in their own words what they need to know or do, we will also ensure they understand the study and, whenever needed, re-explain to them about the study procedures and risk of participating in the trial. After obtaining informed consent, and Dilapan-S® is successfully placed (see section 4.2) and after 30 minutes period of observation, subjects who remain eligible will be randomized to management as inpatient versus outpatient (see section 4.3).

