### **5.3. Randomization**

After Dilapan-S® placement, and if the subject remains eligible, subject will be randomized to the outpatient group or the inpatient group. A confidential computer-generated simple randomization scheme will be prepared and provided by independent vendor (PharmTest, s.r.o., Czech Republic) to our study coordinator. The currently used randomization code will be replaced by 2 randomization codes, 1 of them for CUMC site (both clinics will use the same randomization sequence. The randomization envelopes to be used at CUMC will be provided by UTMB).

A randomization log with group assignment, subject name, and medical record *number* will be used to track the randomization process. The subject will be included in the analysis by intent-to-treat once the randomization assignment has been made.

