#### **5.4.2. Group Assigned to Inpatient Cervical Ripening**

Subjects randomized to inpatient management will be admitted to L&D unit and standard clinical protocol will be initiated for cervical ripening and labor induction. During the period of 12 hours of cervical ripening subject is to remain "nothing per vagina" and undergo continuous fetal heart rate monitoring. During this period, clinical care will be left to the provider's discretion (standard of care at the institution) including "nil per os" or "nothing per os" (NPO) status. No other interventions are to occur during this period of 12 hours, unless clinically indicated. Reasons to remove the dilators and management after 12 hours will be the same as for the outpatient group (see sec. 4.4.1.).

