### **6.2. Secondary Outcomes**

- Rate of vaginal deliveries (%)
- Rate of vaginal deliveries within 24 hours since admission to hospital (%)
- Rate of vaginal deliveries within 36 hours since admission to hospital (%)
- Time from hospital admission to reach active stage of labor defined as  $\geq 6$  cm (mins)
- Time from device placement to reach active stage of labor defined as  $\geq 6$  cm (mins)

- Change in Bishop score from insertion to extraction of device
- Change in cervical dilation after Dilapan-S®
- Rate of spontaneous vaginal deliveries after one round of cervical ripening (%) (no additional medical or mechanical interventions)
- Rate of operative vaginal deliveries (%)
- Rate of caesarean deliveries (%)
- Rate of artificial rupture of membranes (AROM) (%)
- Rate of epidural analgesia (%)
- Total duration of Dilapan-S® application (insertion to removal/extraction) (mins)
- Device placement to delivery interval (mins)
- Induction (Oxytocin/Prostaglandin initiation) to delivery interval (mins)
- Analgesia used during device placement (%), cervical ripening (%) and labor induction (%)
- Rate of adverse neonatal outcomes (composite and individual) –Apgar score <7 at 1-5-10 minutes, Cord arterial pH <7.1, neonatal ICU admission (%)
- Occurrence of maternal and neonatal complications within 2 weeks after delivery (%)
- Total duration of maternal hospital stay (hours)
- Subject reported clinical outcomes (sleep, rest, pain, activities of daily living, etc.) (Appendix 3)
- Subject reported satisfaction with Dilapan-S® treatment (Appendix 3)
- Medicaid charges for each hospitalized subject in both arms

*(Blood Bank Transfusion Operations, Chemistry Division, Hematopathology Division, JSH Labor & Delivery unit, Materials Management, Microbiology Division, Mother Baby Unit, Pharmacy, Respiratory Care Services, Surgical Operating Suite)*

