## **11. Procedures to Maintain Confidentiality**

Each subject will be assigned a study number (Subject ID) with personally identifiable information deleted or removed. This Subject ID will be unique for every subject and will not contain any study group identifier. Subjects' information will be de-identified and tagged with a number. Data will be collected and stored on a UTMB or CUMC password-protected computer in a locked room.

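### Uncertain complication outcomes are finally decided by an unmasked investigator who may confer with the others; the planned second investigator could decide masked at little cost

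*Combined protocol and SAP*

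**What the plan says.** Section 5.5 sets out three steps. First, "Trained and experienced research staff will be responsible for all research data abstraction". Second, "The PI and collaborators will review and validate the outcomes". Third, for an uncertain outcome, "a second investigator will review the chart, discuss with the other investigators as needed, and make a final determination regarding the outcome". None of the three mentions masking, and the available text provides no independent adjudication committee.

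The outcomes that pass through these steps include, in section 6.2, "Occurrence of maternal and neonatal complications within 2 weeks after delivery". That list gives no diagnostic criteria for them. The data items in section 3 also cover infections, haemorrhage, and complications of device placement, ripening, labor and delivery. Sections 5.6 and 5.7 say that the two-week data come from charts or, failing that, by telephone.

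Several places bear on whether the deciders can know the arm:

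- Section 5.1: "The principal investigator, study coordinator, or a collaborator will be responsible for the informed consent".
- Section 5.3 keeps "A randomization log with group assignment, subject name, and medical record" number together in one log.
- Section 5.4.2: "Subjects randomized to inpatient management will be admitted to L&D unit", with continuous fetal monitoring over the ripening period. Under section 5.4.1 the outpatient arm leaves and comes back.
- Section 11 says the subject ID "will not contain any study group identifier". Section 10.2 stores data by ID code, keeps the linking log separately, and adds monitoring by a sponsor's representative.

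**The concern.** Uncertain cases are where knowledge of the arm can most easily tip a decision. Section 5.5 recognises that such cases will occur and plans a second reader for them, but has that reader use the chart and allows discussion with the other investigators before the decision.

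The protocol also records what it expects. Section 3 anticipates no significant adverse effects of outpatient compared with inpatient use, and section 12 hopes for a shorter stay with maternal and neonatal outcomes unaffected. The second half of that message rests partly on complication counts that will be small. The cost-minimization analysis in section 3 likewise presupposes equal effectiveness. A systematic error in classifying complications cannot be repaired in the analysis.

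**Working it through.** **Can the deciders know the arm?** The documents never say so in words; it follows from several sections together. Investigators obtain consent (5.1), a study log ties the assignment to the woman's name and record number (5.3), and the two arms leave different traces in the chart (5.4.1, 5.4.2). The second investigator is told to read that chart. An ID without a group code masks the data file, not the chart. Nothing in section 10.2 says that the sponsor's monitor is masked or decides outcomes.

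**Which outcomes leave room for judgement?**

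| Little room | Room for judgement |
|---|---|
| Stay over 48 hours (primary), mode of delivery, Apgar score, cord pH, NICU admission, durations, charges | Maternal infection, haemorrhage, other maternal and neonatal complications |

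**Design figures.** With 0.54 versus 0.378, two-sided alpha 0.05 and 85% power (section 13.4), the usual two-proportion formula without continuity correction gives 169 per group. Then 169 / 0.90 = 187.8, so 188 per group and 376 in total. The stated figures are reproduced, and nothing below changes them.

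**How many events?** The registry table in section 3 gives maternal infection in 14 of 444 women, 3.2%. Expected per arm: 0.032 × 188 = 6.0.

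**What reclassification could do (assumed cases).** With 188 per arm the risk ratio is the ratio of counts, and p comes from the planned chi-square test, uncorrected:

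| Outpatient v inpatient events | Risk ratio | p |
|---|---|---|
| 6 v 6 | 1.00 | 1.00 |
| 4 v 6 (two outpatient cases ruled out) | 0.67 | 0.52 |
| 9 v 6 | 1.50 | 0.43 |
| 7 v 6 (two outpatient cases ruled out) | 1.17 | 0.78 |

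**Range over an assumed undercall.** Let the true rate be 3.2% in both arms and let a fraction m of true outpatient events be ruled no event. The observed outpatient rate is 0.032 × (1 − m):

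| m | Outpatient rate | False gap (points) | Expected events, outpatient v inpatient |
|---|---|---|---|
| 10% | 2.9% | 0.3 | 5.4 v 6.0 |
| 20% | 2.6% | 0.6 | 4.8 v 6.0 |
| 30% | 2.2% | 1.0 | 4.2 v 6.0 |
| 50% | 1.6% | 1.6 | 3.0 v 6.0 |

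A true excess would shrink in the same way. With true rates of 6.4% versus 3.2% and m = 20%, the observed excess is 0.064 × 0.80 − 0.032 = 1.9 points instead of 3.2. The documents give no value for m. An overcall in the outpatient arm, by an investigator anxious about safety, would push the other way.

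**The case against.** The strongest case against runs as follows.

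- **Reach.** Diagnosis and charting are done first by the managing obstetrical team, who cannot be masked to where ripening took place. Masking one reader for a few uncertain cases leaves that source of bias in place. This stands.
- **Scope.** The named neonatal composite consists of recorded values and events, and the primary outcome rests on admission and discharge times. This also stands; the point is confined to judged complications.
- **Size.** The shift from 1.0 to 0.67 needs two borderline cases, a third of that arm's infections, both outpatient and both ruled the same way. None of the scenarios changes the planned test result, and the documents set no safety margin or powered safety hypothesis for such cases to tip. A reader might infer that one or two borderline decisions settle whether outpatient ripening looks as safe as inpatient. The documents do not support that: the estimate moves, but its uncertainty at these counts is already wide.
- **Knowledge of the arm.** It is inferred, and data are held under an arm-free ID. This lowers certainty only slightly, because the deciding document is the chart. The text between sections 3 and 5 was not available to check.
- **Feasibility.** Removing all notes from the ripening phase would make ripening complications, such as bleeding or tachysystole, impossible to judge. That rules out wholesale removal, but not redacting the place of ripening while keeping the findings. A masked decision also needs written definitions, which section 6.2 does not give for complications.

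One might also object that a masked reader means extra staff. With two sites, UTMB and CUMC, an investigator from the other site could serve, if one is available.

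**Conclusion.** The concern holds for judged secondary complications. Section 5.5 leaves the final decision on uncertain cases to an investigator who can see the arm in the chart and may first confer with others who know it. This can bias the comparison of maternal infection, haemorrhage and other two-week complications.

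It would go too far to conclude that the trial's results, or its primary outcome, are compromised, or that bias toward the expected result has been shown. Size and direction cannot be derived from the documents, and the figures above rest on assumed numbers of borderline cases. The sample size of 376 and the 85% power are untouched. This is a worthwhile, inexpensive improvement to secondary-outcome review, not a flaw in the main conclusion.

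**What to change.** In section 5.5, and for the data collected under 5.6 and 5.7, state that:

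1. Uncertain complication outcomes are decided by the second investigator already planned, chosen as one who did not enrol or manage the woman, for example from the other site.
2. That investigator works from an extract with the allocation and the place of ripening redacted but the clinical findings kept, including those during ripening.
3. Definitions for each judged complication are written before review starts, and the decision is made against them.
4. The decision is recorded before any discussion with unmasked investigators.
5. The abstractor refers a case whenever the chart neither clearly meets nor clearly fails the definition, by the same rule in both arms. Referral is not left to the validators' discretion.

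The cost is protocol wording, the work of writing definitions, and coordinator time to redact extracts for the uncertain cases. Masking will be imperfect, because timings or monitoring records may hint at the arm. Bias in the original charting by caregivers, who know the arm, is not addressed and should be acknowledged as a limitation.

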#### **5.6. Post-partum data collection**

Maternal and neonatal outcomes will be assessed following delivery, as detailed in section 5. Subjects will be encouraged to call the research team with any concerns. Data collection forms will be used during these processes and charts will be reviewed. Subjects' direct participation will end after her discharge home from the hospital, however, data on postpartum infections or hospital readmission will be collected from medical charts 2 weeks after subject's delivery.

### **5.7. Follow-up**

No extra postpartum follow-up visits will be performed. Neonatal and maternal outcomes will be collected up to two weeks postpartum and documented in the relevant data collection forms. If these outcomes are not obtainable by chart review, all attempts will be made to obtain relevant outcomes from subject by phone. These will be reported as missing data, if unable to be reached by four weeks after delivery.

## **5.8. Premature Terminations**

### **5.8.1 Screening failure**

A subject who is screened and consented, but Dilapan-S® isn't placed will be considered a screen failure.

### **5.8.2 Early (or premature) termination**

A study subject will be discontinued from participation in the study if any of the following occurs:

- Medical condition or situation occurs such that continued participation in the study would not be in the best interest of the subject in the opinion of the treating investigator.
- Subject wishes to end her study participation prematurely for any reason.
- Lost to follow-up before reaching primary outcome (e.g. did not return from outpatient ripening).

### **5.8.3 Rules for consent withdrawal**

If a subject withdraws her consent to participate in the study, all efforts will be made to discuss with the subject that despite the withdrawal, as many data as possible will be collected, such as safety data, AEs, SAEs. In such circumstances or situations, no data will be collected from the moment of her consent withdrawal, however, data collected before the withdrawal will be kept.

The subject can still request the deletion of such data at any time, but the subject will need to request it in written for proper documentation.

Subjects who will either withdraw their consent or end their participation in the study prematurely will not be replaced. Data obtained will be assessed within ITT population analysis.

## **6. Study Outcomes**

### **6.1. Primary Outcomes**

Rate of hospital stay longer than 48 hours (from admission to discharge)

### **6.2. Secondary Outcomes**

- Rate of vaginal deliveries (%)
- Rate of vaginal deliveries within 24 hours since admission to hospital (%)
- Rate of vaginal deliveries within 36 hours since admission to hospital (%)
- Time from hospital admission to reach active stage of labor defined as  $\geq 6$  cm (mins)
- Time from device placement to reach active stage of labor defined as  $\geq 6$  cm (mins)

- Change in Bishop score from insertion to extraction of device
- Change in cervical dilation after Dilapan-S®
- Rate of spontaneous vaginal deliveries after one round of cervical ripening (%) (no additional medical or mechanical interventions)
- Rate of operative vaginal deliveries (%)
- Rate of caesarean deliveries (%)
- Rate of artificial rupture of membranes (AROM) (%)
- Rate of epidural analgesia (%)
- Total duration of Dilapan-S® application (insertion to removal/extraction) (mins)
- Device placement to delivery interval (mins)
- Induction (Oxytocin/Prostaglandin initiation) to delivery interval (mins)
- Analgesia used during device placement (%), cervical ripening (%) and labor induction (%)
- Rate of adverse neonatal outcomes (composite and individual) –Apgar score <7 at 1-5-10 minutes, Cord arterial pH <7.1, neonatal ICU admission (%)
- Occurrence of maternal and neonatal complications within 2 weeks after delivery (%)
- Total duration of maternal hospital stay (hours)
- Subject reported clinical outcomes (sleep, rest, pain, activities of daily living, etc.) (Appendix 3)
- Subject reported satisfaction with Dilapan-S® treatment (Appendix 3)
- Medicaid charges for each hospitalized subject in both arms

*(Blood Bank Transfusion Operations, Chemistry Division, Hematopathology Division, JSH Labor & Delivery unit, Materials Management, Microbiology Division, Mother Baby Unit, Pharmacy, Respiratory Care Services, Surgical Operating Suite)*

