### **5.4. Pre-Induction**

#### **5.4.1. Group Assigned to Outpatient Cervical Ripening**

After Dilapan-S® placement, subject will be monitored for at least 30 minutes. If no contraindications, such as tachysystole, active vaginal bleeding, rupture of membranes or nonreassuring fetal testing (defined as minimal or absent variability, abnormal baseline, or presence of decelerations) evidence of labor, or other serious medical conditions deemed by the clinical staff or the attending physician to preclude outpatient cervical ripening develop after insertion, the subjects will be randomized. After randomization subject will record the pain she experienced during insertion in the patient's survey (see Appendix 3). Those subjects randomized to outpatient ripening will be given the option to either stay in a hotel or, if they are able to reach the hospital within 60 minutes, return home. The cost for the hotel will be covered by the study budget. Subjects at CUMC will solely be given the option to stay at home. Subjects will be allowed to ambulate, shower and perform regular activity during that period. "Nothing per vagina" will be allowed (incl. intercourse, tampons etc.). Subjects will also be instructed to return to L&D unit 12 hours after insertion, or earlier if any excessive bleeding, rupture of membranes, pain or other concerns (contractions, decreased fetal movement) develop before the 12 hours. Special leaflet (Appendix 2) will be provided to subjects leaving the hospital, with detailed instruction, emergency contacts to appropriate study/clinical staff and space to document of oral medication taken for pain relief (acetaminophen). Subject will also document the date and time of membrane rupture if applicable.

Reasons for examining or removing dilators earlier include but are not limited to:

- 1) Spontaneous onset of labor  
(defined as regular, firm, uterine contractions with an effaced cervix >80% and a cervical dilatation > 3 cm)
- 2) Other than category I fetal heart rate tracing  
(category I includes all: Baseline rate: 110–160 beats per minute, baseline FHR variability: moderate, absent late or variable decelerations, Early decelerations: present or absent and accelerations: present or absent)
- 3) Spontaneous rupture of membranes or need for amniotomy
- 4) Spontaneous expulsion of Dilapan-S® rods
- 5) Subject removed the rods herself

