After the designated 12 hours' time or earlier, if indicated, subjects are to return and to be admitted to L&D unit for standard protocol of labor induction. If the cervix remains unfavorable after extraction or spontaneous expulsion of the dilators (< 3cm and at most 60% effaced), additional mechanical or pharmacological cervical ripening may be provided at the provider's discretion. The agent/type will be recorded into the data sheet.

If subject does not return in the designated time and date as instructed (12 hours window), all attempts will be made to contact the subject by phone or supporting contact person. Subject will also be instructed that if she presents to another hospital, she needs to inform the clinical staff seeing her that she is participating in a trial and that Dilapan-S® was placed for cervical ripening, and to present the study card. We will also do our best to obtain our primary outcome through release of records.

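### Vaginal delivery within 24 h and 36 h is timed only from admission, which falls up to about 12 h later after insertion for outpatients, so both rates favour the outpatient arm even with no effect

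*Combined protocol and SAP*

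**What the plan says.** Section 6.2 starts the clock for two delivery rates at admission: "Rate of vaginal deliveries within 24 hours since admission to hospital" and "Rate of vaginal deliveries within 36 hours since admission to hospital". Section 3 words them the same way. A third outcome, "Time from hospital admission to reach active stage of labor defined as" at least 6 cm, uses the same clock, but Section 6.2 pairs it with a version timed from device placement. The list also has the interval from placement to delivery, in minutes. It has no vaginal delivery rate by 24 or 36 hours from placement or randomisation.

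The two arms are admitted at different points:

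- **Both arms** (Section 5.1): the dilator is placed, and "after 30 minutes period of observation, subjects who remain eligible will be randomized to management as inpatient versus outpatient".
- **Inpatient** (Section 5.4.2): "Subjects randomized to inpatient management will be admitted to L&D unit", and the 12 hours of ripening follow in hospital.
- **Outpatient** (Section 5.4.1): "Subjects will also be instructed to return to L&D unit 12 hours after insertion, or earlier" if problems arise; after that time, or sooner if indicated, "subjects are to return and to be admitted to L&D unit for standard protocol of labor induction".

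Section 13.3 analyses nominal secondary outcomes as Section 13.2 analyses the primary, that is by chi-square in the ITT population.

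**The concern.** Time zero for these rates is set by the randomised assignment. Ripening falls inside the clock for inpatients and outside it for outpatients, so two women with identical courses from insertion to delivery can be classified differently only because of their arm.

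Section 1 states the aim as comparing efficacy and safety, and Section 3 places these rates among the clinical outcomes without marking them as hospital-use measures. A reader would probably take a higher outpatient rate at 24 hours as evidence that outpatient ripening leads to faster or more successful induction. The result could also conflict with the placement-timed intervals in the same list, and the plan does not say which should be believed.

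**Working it through.** **1. The plan's own figure.** The documents give no figure for the 24 h and 36 h rates. The per-arm number used below is the one in Section 13.4, for 0.54 v 0.378, 85% power and two-sided 0.05. With pooled variance under the null and mean proportion 0.459:

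n = [1.960 × √(2 × 0.459 × 0.541) + 1.036 × √(0.54 × 0.46 + 0.378 × 0.622)]² / 0.162² = 168.3, so 169 per arm.

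169 / 0.90 = 187.8, so 188 per arm and 376 in total. The plan's numbers reproduce.

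**2. When each window closes, in hours from insertion.** Admission is at 0.5 h (inpatient) and at up to 12 h (outpatient).

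| Outcome | Inpatient | Outpatient, return at 12 h | Extra time |
|---|---|---|---|
| 24 h from admission | 24 + 0.5 = 24.5 | 24 + 12 = 36 | 11.5 |
| 36 h from admission | 36 + 0.5 = 36.5 | 36 + 12 = 48 | 11.5 |

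If inpatient admission is dated at insertion, the extra time is 12 h. Early return reduces it. This step uses only the protocol and fixes the direction of the bias.

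**3. Size with no true effect.** Give both arms the same distribution F of time from insertion to delivery and the same overall vaginal delivery proportion v. For window W and admission at a hours after insertion:

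rate = v × F(W + a), with F(t) = Φ(ln(t / median) / log-SD).

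Assumptions that are not in the documents: F lognormal, median 20, 24, 28 or 32 h, log-SD 0.30 or 0.45, v 0.70 or 0.80. That makes 16 scenarios per gap.

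Worked case, 24 h rate, median 24 h, log-SD 0.30, v = 0.80:

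- Inpatient: ln(24.5/24)/0.30 = 0.069; Φ = 0.527; × 0.80 = 42.2%.
- Outpatient: ln(36/24)/0.30 = 1.352; Φ = 0.912; × 0.80 = 72.9%.
- Difference: about 31 points.

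With log-SD 0.45 the 24 h rates are 41.5% v 65.3%, a difference of about 24 points. The 36 h rates are 73.5% v 79.2% (log-SD 0.30) and 65.9% v 75.1% (log-SD 0.45), differences of about 6 and 9 points.

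**4. Chance of a significant result with no effect.** Exact binomial enumeration of the uncorrected chi-square test, two-sided 0.05, 169 per arm. Ranges are over the 16 scenarios.

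| Admission after insertion (in, out) | 24 h: difference, points | 24 h: rejection | 36 h: difference, points | 36 h: rejection |
|---|---|---|---|---|
| 0 h, 12 h | 17.3–39.6 | 89.9–100% | 1.6–20.7 | 6.3–97.8% |
| 0.5 h, 12 h | 15.7–37.7 | 84.6–100% | 1.4–19.4 | 6.1–96.1% |
| 0 h, 6 h | 11.1–23.0 | 53.4–99.4% | 1.3–13.2 | 5.8–70.4% |
| 0.5 h, 6.5 h | 10.6–22.7 | 50.2–99.2% | 1.2–12.7 | 5.7–67.0% |

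The last two rows let every outpatient return at about 6 h, to test what early return could do.

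A separate calculation with other spreads (median 20–30 h, log-SD 0.4–0.5, 11.5 h gap) gave 16–30 points at 24 h (rejection 82% to over 99%) and 4–15 points at 36 h (11–83%).

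**5. With a common origin.** If both clocks start at placement or randomisation, a is the same in both arms. The expected difference is then 0 and rejection returns to about 5%.

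**The case against.** The best defence is that the admission clock is deliberate. The trial asks whether outpatient ripening shortens hospital stay, the primary outcome in Section 6.1 is itself counted from admission, and moving ripening out of hospital is the intervention. In-hospital time to vaginal delivery is a coherent companion to that outcome. This stands as a reason to keep the admission-based rates. It does not make them comparisons of how induction went, and the plan does not label them as hospital-use measures.

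Second, much of the safeguard already exists: time from placement to 6 cm, the placement-to-delivery interval, and overall vaginal and caesarean rates. Slower labour would show there. That is right and limits the harm, but none of these gives vaginal delivery by a fixed time from a common origin.

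Third, the 36-hour case is weaker. At the 11.5 h gap, 8 of the 16 scenarios exceed 50% rejection; at a 6 h gap only 2 of 16 do. The direction holds, but material distortion at 36 hours depends on the assumptions.

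Fourth, the plan gives no exact timestamp for admission. If the insertion visit counted as admission for outpatients, the gap would vanish. Section 5.4.1, however, places their admission at return.

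**Conclusion.** The concern holds. As written, the 24-hour and 36-hour vaginal delivery rates give outpatients up to 11.5–12 h more time from insertion, and the planned test makes no allowance for it. That much needs no outside assumption.

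The sizes rest on the assumed lognormal times, vaginal delivery proportions and a single return time for all outpatients. On those, return at 12 h produces a false advantage of about 16–40 points at 24 hours, usually significant, and about 1–21 points at 36 hours, from negligible to large. With a 6 h gap the 24-hour advantage is still about 11–23 points.

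The primary outcome, for which hospital time is the question, and the sample size are not affected. This should be fixed, but it does not threaten the main result.

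**What to change.** In Section 6.2 and the SAP:

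1. Add vaginal delivery within 24 h and within 36 h of device placement (or of randomisation), same origin in both arms, with all women in the arm as denominator. Treat these as the efficacy versions.
2. Treat the placement-timed version of time to 6 cm as the main one.
3. Keep the three admission-timed outcomes, labelled as descriptive hospital-use measures and not as evidence on induction efficacy.
4. State which recorded time counts as admission in each arm.

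**Cost:** a protocol and SAP amendment, made before database lock, with the two new rates reported as added by amendment. No new data are needed, because Section 3 already collects the date and time of device placement and of delivery.
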